6.3 SECONDARY OUTCOMES

Details for assessing all secondary outcomes, including the qualitative outcomes are given in the Supplementary Materials.

6.4 OUTCOME ASSESSMENT SCHEDULE

An overview of the outcome assessment schedule is given in **Table 2**.

Free sugar intakes and adherence will be assessed throughout the intervention period as given in **Table 1**. All other outcomes will be assessed at baseline and at trial end, with the exception of the following: sweet liker status, PROP taste sensitivity and demographic characteristics will be measured only at baseline; questions on adherence and difficulties will be asked at weeks 4, 8 and 12.

All participants will undertake all measures, in the same manner, regardless of intervention arm. Dietary assessments, questions on adherence and difficulties will be undertaken via the Nutritics software. Self-report questionnaires will be administered online via Qualtrics. Measures associated with taste status and appetite will be presented to participants using a paper format to be completed during a test session.

Compliance with trial measures will be enhanced using a bogus pipeline method (Hugh, 2013; Muhlheim et al., 1997; Reid et al., 2014); participants will be asked to provide a saliva sample at baseline and at trial end, for the supposed purpose of examining salivary enzymes that may vary with dietary change. In reality, samples will be discarded. Only at the end of the trial will participants be informed that their samples have not been analysed.

Table 2: Schedule of enrolment, interventions and assessments

	Trial period						
	Enrolment	Baseline	Intervention			End	
Time point	Wk -1 / 2	0	Wk 1	Wk 2	Wk 4	Wk 8	Wk 12
Enrolment							
Eligibility screen	X						
Informed consent	X						
Allocation		X					
Intervention							
Intervention groups							→
Control group							→
Assessments							
24hr diet diary							→
3 day diaries	X	X					X
Adherence							→
Adherence questions					X	X	X
Anthropometrics		X					X

Sweet liker status		X					
PROP taste test		X					
Sweet taste test		X					X
Sweet food choice		X					X
Sweet attitudes		X					X
TFEQ		X					X
FCQ		X					X
Demographics		X					
Knowledge		X					X
GSLTPAQ		X					X
SF36		X					X
Adverse events							→
Difficulties / Adverse events					X	X	X
Interview			X*	X*	X*	X*	X*
BP cheek swab	X						X

X* Interviews completed only once. TFEQ: Three-factor eating questionnaire; FCQ: Food choice questionnaire; GSLTPAQ: Godin- Shepard leisure time physical activity questionnaire; SF-36: Short-form 36 measure of quality of life; BP: Bogus pipeline method.

7 PROCEDURE

7.1 TRIAL SETTING

[figure not shown]
The trial is based in the United Kingdom and run from Bournemouth University. Recruitment started in April 2021 with testing commencing in May 2021. The trial will run for a total period of 18 months, over the year to ensure against seasonal effects, but we anticipate increased recruitment at certain times of the year (January - February and May – July). The trial will not continue over the Christmas period to avoid potential effects as a result of festive intakes.

7.2 RECRUITMENT AND ENROLMENT

Potential participants will be recruited via: personal contacts; University contacts and outlets, including a participant pool; contacts with local groups, e.g. church groups, adult education groups; social media advertising and flyers in local public buildings, e.g. libraries; advertising in local news outlets; and flyers at local eating establishments. The study will be marketed to participants as '*An investigation of the impacts of different dietary recommendations on diet*'.

All potential participants will be asked to complete the informed consent, eligibility form and a 3-day diet diary before being invited to participate. Eligible participants will then be scheduled for a baseline assessment, and following the completion of all baseline measures, participants will be randomised. The process from recruitment to enrolment is shown in Figure 1. The 3-day diet diary for eligibility will also serve as an opportunity to train participants, to allow participants to gauge the commitment required for the study and to ensure participants are competent in the diet diary data collection methods prior to their completion of baseline measures. Participants will not be recruited into the trial until they are comfortable with the commitment and diet diary data collection methods.

Figure 1: Participant flow diagram

7.3 PARTICIPANT TESTING

Baseline and end assessments will be conducted in a single session for all participants. Sessions will last approximately 30-60 min., and will be conducted at Bournemouth University where possible, or in the participant's home via Zoom. 'At-home' test sessions will be used if participants are unable or unwilling to come to the University, and are intended primarily to allow the trial to continue during the COVID-19 pandemic when National lockdown measures and precautions were recommended in the UK (March 2020 - July 2021). These home test sessions may also open the trial to participants who would otherwise be unable to take part, primarily due to location, enhancing study inclusivity. Participants will be tested in the same location at both baseline and trial end, as possible.

All participants will complete the same measures regardless of their completion of test sessions at the University or 'at-home', with a few exceptions: Participants who are tested 'at-home' will not undertake the sweet taste perception and preference tests, the sweet food choice test, nor the solution-based measures of sweet liker status. Participants who are tested 'at-home' will also complete their own anthropometric measurements, but they will do this while the trial researcher observes via Zoom. Comparability across all measurements will be facilitated by involvement of the same researcher both at the University or 'at-home'.

All sessions will commence before 11am to allow individuals to undertake the measures in a fasted state, and will begin at the same time at baseline and trial end. The day before testing participants will also be asked to consume no alcohol, to consume nothing after 10pm, and to undertake no heavy exercise. Measures will be undertaken in the same order during each test session, as follows, or simply omitted: anthropometry; saliva sample; sweet liker status; PROP taste test; sweet taste test; and sweet food choice test. All questionnaires will be completed and checked for completion before the test session.

7.4 WITHDRAWAL AND DEBRIEFING

Participants will be considered as having withdrawn from the trial if they either express this or they do not attend the final test day. If individuals fail to report diet diaries, they will be sent reminders however, data will be noted simply as 'missing' while the participant continues in the trial.

Individuals will be debriefed on exit, or at their original 12-week intervention end time-point if other household members are partaking. During the debrief session, participants will be asked for their understanding of the trial purpose to investigate the success of the methods to disguise the trial aims, and will then be debriefed on the true purpose of the trial. Following the debrief session, participants will be offered a consultation on their diet, by a Registered Associate Nutritionist, as a thank you for taking part.

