4.3 RANDOMISATION

Participants will be allocated into one of four trial arms following baseline assessments, using stratified randomisation (Suresh, 2011), based on gender, BMI, and free sugar intakes (%TEI) at baseline, as variables that may affect our outcomes. Randomisation will be undertaken by a researcher with no direct contact with participants using a random number generator, before the trial start. Group allocations will be concealed using opaque envelopes.

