5.2 BLINDING

All envelopes containing the intervention information will be identical, sealed and coded by the researcher undertaking the randomisation. The researcher in direct contact with participants will be kept blinded to treatment allocation throughout data collection. It is impossible to blind participants, however, participants will be blinded to the true purpose of the trial and to other interventions used. To further disguise the purpose of the trial, all participants will complete several questionnaires in addition to those focusing on sugar.

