8.1 ANALYSES ONE: EFFECTS OF THE DIFFERENT DIETARY RECOMMENDATIONS

To test the effects of the different dietary recommendations, a series of multiple regression analyses will be run. A separate analysis will be run for each outcome variable, where the outcome at week 12 will be predicted by trial arm (intervention/control) and outcome variable at baseline. Additional independent variables will also be included in each analysis as possible, to include: demographic variables, total energy intakes, sweet liker status; PROP taster status; and attitudes to sweet foods, eating behaviour and food choice.

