Three distinct analyses were pre-specified in advance: 1) Analyses of the population as a whole to investigate the effects of the three different types of dietary recommendation versus control; 2) Analyses of the effects of the dietary recommendations in different population subgroups, and 3) Investigation of the barriers and facilitators to success.

Data presentation

Data will be presented as mean \pm standard deviation in all cases, unless stated. Values will be considered significant at the $p<0.05$ level. Before completing analyses, data will be checked for normality. The data set is large, $N=242$, thus a normal distribution will be assumed. Where assumptions of homogeneity of variance are violated (Levene's test $p<0.05$), statistics will be taken from analyses conducted assuming non-equal variances. Bonferroni corrections for multiple testing will be applied to data where tests were not pre-specified in the study protocol. Where multiple regression analyses are used, all variables will be checked for multicollinearity using correlation cut-offs of <0.7 . Pearson correlation values will be used for all continuous variables, and Spearman correlations for categorical variables.

Participant characteristics

Details of study completion will be provided and a CONSORT diagram created detailing number randomized to each group, number completing the study in each group, drop out and number included in all analyses.

Characteristics will be given for the whole sample and for each trial group.

Analyses One: Quantitative Data

For analyses one, multiple regression analyses will be used. Analyses will be conducted for both primary outcomes, for key secondary outcomes - daily energy intake, sugar-sweetened food intake, LCS-sweetened food intake, body weight, waist circumference, and adverse events; and change (baseline - week 12) data for these outcomes; and for other secondary outcomes (dietary

composition, sweet food perceptions and preferences, sweet food choice, attitudes to sweet foods, attitudes towards eating behaviour, motives for food choice, knowledge and lifestyle variables, quality of life) if differences are found in the sample as a whole from baseline to week 12. This will reduce the number of exploratory tests undertaken. Differences from baseline to week 12 will be investigated by paired t-tests. Primary outcomes and outcomes associated with dietary composition will also be investigated in the same manner at weeks 1, 2, 4 and 8.

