Primary models will include gender, age, control/intervention group, baseline %FS, baseline body weight (as randomization variables), and baseline variable of interest. In analyses for %FS, sugar-sweetened food intake, LCS-sweetened food intake, body weight and waist circumference, TEI at Week 12 and physical activity at Week 12 will also be included. Secondary models will also include any additional variable that correlates with each outcome when assessed independently. All variables measured will be considered as secondary variables. Effects for all continuous variables will be investigated using linear multiple regression. Effects for adherence will be investigated using logistic regression to predict adherent vs not adherent.

Analyses Two: Quantitative Data

For analyses two, analyses one will be repeated for demographic groups where significant associations for these variables were found in analyses one. Analyses will only be conducted if significant associations are reported. If no significant associations with demographic variables are found, these analyses will not be completed. These analyses are intended to demonstrate differing effects of the intervention/s in different population groups.

Analyses Three: Qualitative Data

Analyses three will investigate the qualitative data collected from a subset of participants using solo interviews. These interviews were scheduled for completion in a sample of 80 participants from different intervention groups and at different time points. These analyses will be undertaken using a thematic framework analysis. First, a random sample of interviews will be analysed inductively using thematic analysis to identify codes. These codes will be used to create a framework and the framework then applied to all interviews.

Framework analysis has been chosen as a suitable analytical method for evaluating the qualitative interview data gathered, due to an interest in individual experiences and seeks to identify the different factors (barriers or facilitators) that contributed to successful or unsuccessful dietary change (Braun & Clark, 2013). The practical methods for conducting framework analysis follow a methodology as outlined below.

Framework analysis (Braun & Clarke, 2006; 2013; Gale et al, 2013).

Phase 1 'Familiarizing yourself: Transcribing data (if necessary), reading and re-reading the data, noting down with your data: initial ideas'.

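### Housemates may take part together, but the plan does not say how they are allocated and no analysis allows for it; the likely effect is a modest dilution of the comparison with control (minor)

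*Protocol*

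**What the plan says.** **Co-enrolment is foreseen.** Protocol section 7.4 debriefs participants on exit, or "at their original 12-week intervention end time-point if other household members are partaking". The eligibility criteria in section 4.1 do not limit enrolment to one person per household. Section 7.2 makes shared households plausible: "Potential participants will be recruited via: personal contacts; University contacts and outlets, including a participant pool", along with local groups.

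**Allocation is described per participant.** Section 4.3 stratifies "based on gender, BMI, and free sugar intakes (%TEI) at baseline". It does not mention households.

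**Arms are assumed to be separate.** Sections 5.1.1 to 5.1.5 describe the interventions as printed pages in a sealed envelope. The control envelope is padded with blank pages and carries a diary instruction worded so that it can pass for advice. Section 5.2 says "participants will be blinded to the true purpose of the trial and to other interventions used".

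**The analyses have no household component.** In protocol section 8.1, "the outcome at week 12 will be predicted by trial arm (intervention/control) and outcome variable at baseline". In the SAP (Analyses One), "Primary models will include gender, age, control/intervention group, baseline %FS, baseline body weight (as randomization variables), and baseline variable of interest". For model type the SAP says "Effects for all continuous variables will be investigated using linear multiple regression", with logistic regression for adherence. Other secondary outcomes are modelled only if the whole sample changes: "Differences from baseline to week 12 will be investigated by paired t-tests".

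**The concern.** The debrief rule shows that the authors saw disclosure within a household as a risk, but they dealt with it only at exit. It does not cover contact during the 12 weeks. It also runs to the leaver's own end date, so a housemate who started later could still be on trial.

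Two separate things are at stake:

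- **Exposure of controls.** Housemates may shop and eat together and can read each other's pages. If one is a control and the other is on an advice arm, part of the effect reaches the control. The difference from control, which is the main comparison, then shrinks.
- **Correlation.** Intakes of housemates are likely to be correlated. Whether this makes a standard error too small depends on how housemates are allocated and on which test is considered.

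**Working it through.** **Inputs from the documents.** Section 4.2 gives a 2-point target, standardised difference 0.8 (so SD = 2/0.8 = 2.5), 80% power, alpha 0.05, 60 per arm and 20% attrition (60 × 0.8 = 48 per arm analysed). There are four equal arms, three of them advice arms.

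**Assumptions, because the documents give no figures.** f is the share of participants with an enrolled housemate, in two-person households. ρ is the within-household correlation of the quantity tested. c is the share of the effect that reaches a control housemate.

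**1. The plan's own sample size.** n = 2(1.96 + 0.84)²/0.8² = 24.5, so 25 per arm, and 25/0.8 = 31.25, so 32 with attrition. The stated 60 does not follow from these inputs but exceeds them. That is a separate matter; here it means there is room to spare. Power at 48 per arm is Φ(0.8 × √(48/2) − 1.96) = 97.5%.

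**2. Exposure of controls (individual allocation).** The chance that a control's housemate is on an advice arm is about 3/4. The fall in the control difference is f × 3/4 × c × 2 points.

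- f = 0.10, c = 0.25: 0.10 × 0.75 × 0.25 × 2 = 0.0375 points, 1.9% of the target. Power at 48 per arm is 97.0%.
- f = 0.30, c = 0.50: 0.30 × 0.75 × 0.50 × 2 = 0.225 points, 11% of the target. Power is 93.5%.
- Extreme case, f = 0.40, c = 1: a true 2-point difference appears as 1.40 points. Power is 78.2%.

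**3. Arm contrast, individual allocation.** For one advice arm against control, a pair is both on advice with probability 1/16, both on control 1/16, and split between the two 2/16. Same-arm pairs add covariance to the variance of the difference and split pairs subtract it: 1/16 + 1/16 − 2/16 = 0. A simulation (240 participants, 20,000 runs) agrees. Type I error is 0.049 at f = 0.2, ρ = 0.3 and 0.049 at f = 0.4, ρ = 0.5. The mean model SE against the true SE is 0.1820/0.1826 and 0.1821/0.1827.

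**4. Arm contrast, housemates in the same arm.** The design effect is 1 + fρ. The SE is too small by 1 − 1/√(1 + fρ), and type I error is 2{1 − Φ(1.96/√(1 + fρ))}.

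| f | ρ | 1 + fρ | SE too small by | Type I error |
|---|---|---|---|---|
| 0.10 | 0.3 | 1.03 | 1.5% | 0.0535 |
| 0.10 | 0.5 | 1.05 | 2.4% | 0.0558 |
| 0.30 | 0.3 | 1.09 | 4.2% | 0.0605 |
| 0.30 | 0.5 | 1.15 | 6.7% | 0.0676 |

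Simulation of same-arm pairs gives 0.058 at f = 0.2, ρ = 0.3 (formula 0.057) and 0.074 at f = 0.4, ρ = 0.5 (formula 0.074).

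**5. Whole-sample paired t-tests.** These test the mean change over everyone, so split pairs no longer cancel. The variance of the mean change is inflated by 1 + fρ under either allocation, and the table applies with ρ taken as the correlation of the changes. At f = 0.30 the type I error is about 6-7%.

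**The case against.** The strongest reply is that the only allocation the documents describe is individual, and step 3 shows that the standard error of the arm contrast is then about right. That stands. A reader might infer from the missing household term that the trial's standard errors are generally too small. The documents do not support this, because it needs housemates to be placed in the same arm and nothing says that they are.

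A second reply is that exposure of controls is conservative, small over the central range, and built wholly on assumed values. That also stands, and it is why the point is minor. It does not make the point empty: bias toward no difference matters when the question is whether printed advice works at all.

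A third reply is that the plan is not blind to such exposure. Section 5.1.5 assesses activities such as information gathering and sweetener use, and section 7.4 asks at debrief what participants understood the trial to be about. These are indirect signs. Neither identifies which controls lived with an advice-arm participant.

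Finally, the Supplementary Materials, the flow diagram and the opening part of the SAP were not available, and a household rule could be there. If so, the allocation part of this point is answered.

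**Conclusion.** The point holds as a minor one. Co-enrolment of housemates is foreseen, their allocation is not described in the available text, and no analysis takes account of it.

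- **Comparison with control:** a conditional bias toward no difference of 0.04-0.23 points, 2-11% of the target. This assumes individual allocation, 10-30% of controls with an enrolled housemate (three quarters of these on advice) and 25-50% spillover.
- **Arm-contrast standard error:** about right under individual allocation. If housemates share an arm and 30% of participants are in two-person households with ICC 0.3-0.5, it is about 4-7% too small and type I error is about 6-7%. At 10% sharing, type I error is at most about 5.6%.
- **Paired t-tests that select secondary outcomes:** mildly anti-conservative under either allocation. A few extra outcomes may pass to modelling. The primary outcomes do not depend on this step.

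A reader might also infer that shared households undermine the sample size. They do not: even at f = 0.4 and ρ = 0.5 with same-arm housemates, the protocol's inputs require 38 per arm, below the planned 60.

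**What to change.** 1. State how members of one household were allocated.
2. Code a household identifier. The documents do not say that one is recorded, but staff cannot apply the section 7.4 debrief rule without knowing who lives together.
3. Report the number of shared households by arm pairing.
4. Use household-clustered standard errors, or GEE with household as the cluster, in the linear and logistic models and in the paired baseline-to-week-12 tests. Pool by Rubin's rules, as the SAP already provides.
5. Add a sensitivity analysis of the primary outcomes that excludes participants whose housemate was allocated to a different arm.

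Item 4 corrects the variance only and cannot remove spillover. Keeping just the first-enrolled member of each household would not do so either, since an exposed control could be the one kept. Item 5 is the analysis that addresses exposure.

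The cost is one column, one re-run and a smaller sample in the sensitivity analysis. With individual allocation the loss is about f × 3/4, so 0.10 × 0.75 × 240 = 18 participants at 10% sharing and 0.30 × 0.75 × 240 = 54 at 30%. If few households are shared, the results barely change and the report can say so.

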8 ANALYSES

The data gathered will contribute to three distinct analyses: 1) Analyses of the population as a whole to investigate the effects of the three different dietary recommendations versus control; 2) Analyses of the effects of the dietary recommendations in different population subgroups, and 3) Investigation of the barriers and facilitators to success. Quantitative data will be analysed using SPSS, on an Intention-to-Treat basis, following checks for the assumptions for parametric data. Qualitative data will be analysed as detailed below.

8.1 ANALYSES ONE: EFFECTS OF THE DIFFERENT DIETARY RECOMMENDATIONS

To test the effects of the different dietary recommendations, a series of multiple regression analyses will be run. A separate analysis will be run for each outcome variable, where the outcome at week 12 will be predicted by trial arm (intervention/control) and outcome variable at baseline. Additional independent variables will also be included in each analysis as possible, to include: demographic variables, total energy intakes, sweet liker status; PROP taster status; and attitudes to sweet foods, eating behaviour and food choice.

